13. APPENDIX 3: RECOMMENDED DOSE MODIFICATIONS FOR BINIMETINIB-RELATED* ADVERSE EVENTS

| Severity of Adverse Event | Dose Modifications | | |
|--|--|--|--|
| Cardiomyopathy | | | |
| Asymptomatic, absolute decrease in LVEF of $> 10\%$ from baseline that is also below the LLN | Withhold binimetinib for up to 4 weeks, evaluate LVEF every 2 weeks. | | |
| | Resume binimetinib at a reduced dose if the following are present: | | |
| | LVEF is at or above the LLN and Absolute decrease from baseline is 10% or less and Patient is asymptomatic. If LVEF does not recover within 4 weeks | | |
| | permanently discontinue binimetinib. | | |
| Grade 3-4 (Symptomatic congestive heart failure or absolute decrease in LVEF of $> 20\%$ from baseline that is also below LLN) | Permanently discontinue binimetinib. Closely monitor LVEF until resolution or up to 16 weeks. | | |
| Venous Thromboembolism | | | |
| Uncomplicated DVT or PE | Withhold binimetinib. | | |
| | If improves to Grade 0-1, resume at a reduced dose. If no improvement, permanently discontinue binimetinib. | | |
| Life threatening PE | Permanently discontinue binimetinib. | | |
| Serous Retinopathy | | | |
| Symptomatic serous retinopathy/ Retinal pigment epithelial detachments | Withhold binimetinib for up to 10 days. If improves and becomes asymptomatic, resume at the same dose. If not improved, resume at a lower dose level or permanently discontinue binimetinib. | | |
| Retinal Vein Occlusion (RVO) | | | |
| Any Grade | Permanently discontinue binimetinib. | | |
| Uveitis | | | |
| Grade 1-3 | If Grade 1 or 2 does not respond to specific ocular therapy, or for Grade 3 uveitis, withhold binimetinib and encorafenib for up to 6 weeks. | | |
| | If improved, resume at same or reduced dose. If not improved, permanently discontinue binimetinib. | | |
| Grade 4 | Permanently discontinue binimetinib. | | |

| Severity of Adverse Event | Dose Modifications | |
|---|--|--|
| Other Eye Disorders (i.e., Non-retinal Events, non-Uveitis Events | | |
| Grade 1-2 | Maintain dose level of encorafenib and binimetinib and increase frequency of ophthalmic monitoring to at least every 14 days until stabilization or resolution. | |
| Grade 3 | Interrupt dosing of encorafenib and binimetinib and refer patient to ophthalmologist within 7 days. | |
| | • If resolved to Grade ≤ 1 in ≤ 21 days, resume treatment at 1 reduced dose level of encorafenib and binimetinib. | |
| | • If not resolved to Grade ≤ 1 in ≤ 21 days, permanently discontinue encorafenib and binimetinib and close follow-up with ophthalmic monitoring until stabilization or resolution. | |
| Grade 4 | Permanently discontinue encorafenib and binimetinib and immediate follow-up with ophthalmic monitoring until stabilization or resolution. | |
| Interstitial Lung Disease | | |
| Grade 2 | Withhold binimetinib for up to 4 weeks. | |
| | If improved to Grade 0-1, resume at a reduced dose. If not resolved within 4 weeks, permanently discontinue. | |
| Grade 3 or Grade 4 | Permanently discontinue binimetinib. | |
| Hepatotoxicity | | |
| Grade 2 AST or ALT increased | Maintain binimetinib dose. | |
| | • If no improvement within 2 weeks, withhold binimetinib until improved to Grade 0-1 or to pretreatment/baseline levels and then resume at the same dose. | |
| Grade 3 or 4 AST or ALT increased | See Other Adverse Reactions. | |
| Rhabdomyolysis or Creatine Phosphokinase (CPK) elevations | | |
| Grade 4 asymptomatic CPK elevation or | Withhold binimetinib dose for up to 4 weeks. | |
| Any Grade CPK elevation with symptoms or with renal impairment | If improved to Grade 0-1 resume at a reduced dose. If not resolved within 4 weeks, permanently discontinue binimetinib. | |

| Severity of Adverse Event | Dose Modifications | |
|---|--|--|
| Dermatologic | | |
| Grade 2 | If no improvement within 2 weeks, withhold until Grade 0-1. Resume at same dose if first occurrence or reduce dose if recurrent. | |
| Grade 3 | Withhold until Grade 0-1. Resume at same dose if first occurrence or reduce dose if recurrent. | |
| Grade 4 | Permanently discontinue binimetinib and encorafenib. | |
| Nausea/Vomiting | | |
| Grade 1-2 | Maintain dose level of encorafenib and binimetinib. Promptly institute antiemetic measure. | |
| Grade 3 | Interrupt dosing of encorafenib and binimetinib until resolved to Grade ≤ 1 . Then resume treatment at 1 reduced dose level of encorafenib. Resume treatment with binimetinib at the current dose if, in the judgment of the Investigator, the toxicity is considered to be unrelated to binimetinib, or at 1 reduced dose level. Note: Interrupt dosing of encorafenib and binimetinib for \geq Grade 3 vomiting or Grade 3 nausea only if the vomiting or nausea cannot be controlled with optimal antiemetics (as per local practice). If unresolved permanently discontinue binimetinib and encorafenib. | |
| Grade 4 | Permanently discontinue binimetinib and encorafenib. | |
| Other Adverse Reactions | | |
| Recurrent Grade 2 or First occurrence of any Grade 3 | Withhold for up to 4 weeks. If improves to Grade 0-1 or to pretreatment/baseline levels, resume at reduced dose. If no improvement, permanently discontinue binimetinib and encorafenib. | |
| First occurrence of any Grade 4 | Permanently discontinue or withhold for up to 4 weeks. If improves to Grade 0-1 or to pretreatment/baseline levels, then resume a reduced dose. If no improvement, permanently discontinue binimetinib and encorafenib. Consider permanently discontinuing binimetinib at | |
| | encorafenib. | |

| Severity of Adverse Event | Dose Modifications |
|---------------------------|--|
| Recurrent Grade 4 | Permanently discontinue binimetinib and encorafenib. |

*For adverse events that may be related to both binimetinib and encorafenib, guidance is provided for the other agent also.

14. APPENDIX 4: ADVERSE EVENTS: DEFINITIONS AND PROCEDURES FOR RECORDING, EVALUATING, FOLLOW-UP, AND REPORTING

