6.6. Dose Modification

6.6.1. Dose Interruptions

Following initiation of therapy, treatment with encorafenib and binimetinib may be delayed to allow resolution of toxicity. Patients may resume treatment if no medical condition or other circumstance exists that, in the opinion of the Investigator, would make the patient unsuitable for further participation in the study.

Individual decisions regarding dose interruptions and modifications should be made using appropriate clinical judgment, considering relatedness of the AE to the study treatment and the patient's underlying condition. Adverse events that have a clear alternative explanation, or transient (\leq 72 hours) abnormal laboratory values without associated clinically significant signs or symptoms may be exempt from dose-reduction rules. The treating Investigator

should refer to and follow the labeled guidance and/or institutional guidelines for the management of toxicities relating to encorafenib and binimetinib. Detailed guidelines can also be found in Appendix 2 and Appendix 3.

Dose interruptions are permitted in the case of medical/surgical events or logistical reasons not related to study treatment (e.g., elective surgery, unrelated medical events, vacation, holidays). Patients should be placed back on study treatment within 2 weeks (14 days) of the scheduled interruption, unless otherwise discussed with the Sponsor. The reason for interruption will be documented in the patient's study record.

If a patient misses > 6 weeks (i.e., 42 consecutive days) of dosing with encorafenib, study treatment with encorafenib will be permanently discontinued. Due to the potential for limited efficacy of binimetinib alone in the study population, if a patient permanently discontinues treatment with encorafenib, they must also permanently discontinue treatment with binimetinib.

If a patient misses > 6 weeks (i.e., 42 consecutive days) of dosing with binimetinib, study treatment with binimetinib will be permanently discontinued. If a patient discontinues treatment with binimetinib, the patient may continue treatment with encorafenib. Due to the potential for increased toxicity when binimetinib is discontinued, doses of single-agent encorafenib may need to be decreased.

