12. APPENDIX 2: RECOMMENDED DOSE MODIFICATIONS FOR ENCORAFENIB-RELATED* ADVERSE EVENTS

| Severity of Adverse Event | Dose Modifications | |
|--|--|--|
| New Primary Malignancies | | |
| Non-cutaneous RAS mutation-positive malignancies | Permanently discontinue encorafenib and binimetinib. | |
| Uveitis | | |
| Grade 1-3 | If Grade 1 or 2 does not respond to specific ocular therapy, or for Grade 3 uveitis, withhold encorafenib and binimetinib for up to 6 weeks. | |
| | If improved, resume at same or reduced dose. If not improved, permanently discontinue. | |
| Grade 4 | Permanently discontinue encorafenib and binimetinib. | |
| Other Eye Disorders (i.e., non-Uveitis Events) | | |
| Grade 1–2 | Maintain dose level of encorafenib and binimetinib and increase frequency of ophthalmic monitoring to at least every 14 days until stabilization or resolution. | |
| Grade 3 | Interrupt dosing of encorafenib and binimetinib and refer patient to ophthalmologist within 7 days. | |
| | If resolved to Grade ≤ 1 in ≤ 21 days, resume treatment at 1 reduced dose level of encorafenib and binimetinib. | |
| | If not resolved to Grade ≤ 1 in ≤ 21 days, permanently discontinue encorafenib and binimetinib and close follow-up with ophthalmic monitoring until stabilization or resolution. | |
| Grade 4 | Permanently discontinue encorafenib and binimetinib and immediate follow-up with ophthalmic monitoring until stabilization or resolution. | |
| QTc Prolongation | | |
| $QTcF > 500 \text{ ms and} \le 60 \text{ ms increase from baseline}$ | 1 st occurrence: | |
| | • Temporarily interrupt dosing of encorafenib until QTcF < 500 ms. Then resume treatment at 1 reduced dose level of encorafenib. | |
| | 2 nd occurrence: | |

| Severity of Adverse Event | Dose Modifications | |
|---|--|--|
| | • Temporarily interrupt dosing of encorafenib treatment until QTcF < 500 ms. Then resume treatment at 1 reduced dose level of encorafenib. | |
| | Permanently discontinue encorafenib and binimetinib. | |
| QTcF > 500 ms and > 60 ms increase from baseline | Permanently discontinue encorafenib and binimetinib. | |
| Hepatotoxicity | | |
| Grade 2 AST or ALT increased | Maintain encorafenib dose. | |
| | • If no improvement within 4 weeks, withhold encorafenib until improved to Grade 0-1 or to pretreatment/baseline levels and then resume at the same dose. | |
| Grade 3 or 4 AST or ALT increased | See Other Adverse Reactions | |

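### For Grade 4 uveitis Appendix 2 stops both drugs but Appendix 3 stops only binimetinib, and Appendix 3 leaves encorafenib's final status unstated when lower-grade uveitis does not improve

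*Protocol*

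**What the plan says.** Uveitis appears in both dose-modification tables, Protocol Appendix 2 (encorafenib) and Appendix 3 (binimetinib).

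- **Grade 4.** Appendix 2: "Grade 4 | Permanently discontinue encorafenib and binimetinib". Appendix 3: "Grade 4 | Permanently discontinue binimetinib", with no mention of encorafenib.
- **Grade 1-3, hold.** Both appendices withhold both drugs. Appendix 3 does so when Grade 1 or 2 fails ocular treatment, "or for Grade 3 uveitis, withhold binimetinib and encorafenib for up to 6 weeks".
- **Grade 1-3, outcome of the hold.** Appendix 2: "If improved, resume at same or reduced dose. If not improved, permanently discontinue", with no drug named. Appendix 3: "If improved, resume at same or reduced dose. If not improved, permanently discontinue binimetinib".

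The footnote to Appendix 3 says: "For adverse events that may be related to both binimetinib and encorafenib, guidance is provided for the other agent also". Section 6.6.1, in its paragraph on missed binimetinib doses, adds: "If a patient discontinues treatment with binimetinib, the patient may continue treatment with encorafenib". It also notes that the single-agent encorafenib dose may have to come down.

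**The concern.** At Grade 4 the two tables give different answers for the same event at the same grade: one stops encorafenib, the other does not mention it. A site that opens only Appendix 3 sees a binimetinib stop, and Section 6.6.1 then permits encorafenib alone. At Grade 1-3 the gap lies inside Appendix 3: two drugs go on hold, and the line that closes a failed hold disposes of only one.

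What is at stake is consistent handling of an eye toxicity across sites. No statistical quantity depends on it.

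**Working it through.** No arithmetic is needed beyond a count. The check sets the rows side by side and then reads them with Sections 6.6.1 and 6.7.

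**1. Is Appendix 3 silent on encorafenib simply because it is the binimetinib table?** List the rows that carry a mandatory permanent stop in both appendices, and note which drugs each names. The recurrent Grade 3 row under other adverse reactions is left out because it only asks that stopping be considered.

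| Row | Appendix 2 names | Appendix 3 names |
|---|---|---|
| Uveitis Grade 1-3, not improved | no drug (after holding both) | binimetinib only |
| Uveitis Grade 4 | both | binimetinib only |
| Other eye disorders Grade 3, not resolved | both | both |
| Other eye disorders Grade 4 | both | both |
| Dermatologic Grade 4 | both | both |
| Nausea/vomiting Grade 4 | both | both |
| Other reactions, recurrent Grade 2 or first Grade 3, no improvement | both | both |
| Other reactions, first Grade 4, no improvement | both | both |
| Other reactions, recurrent Grade 4 | both | both |

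Appendix 3 names both drugs in 9 − 2 = 7 of 9 rows. The dermatologic and nausea/vomiting rows, for example, read "Grade 4 | Permanently discontinue binimetinib and encorafenib". With the footnote's promise about the other agent, this shows that where an event is shared, the binimetinib table normally covers encorafenib too. The two uveitis rows are the exceptions.

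**2. Grade 4.** Appendix 2 stops both drugs and Appendix 3 stops one. Section 6.6.1 permits encorafenib after a binimetinib stop. Section 6.7 lists Grade 4 events, as set out in the two appendices, among the reasons to stop all study treatment unless the Sponsor approves otherwise. Two provisions therefore point to stopping both drugs, although Section 6.7 does so by reference to tables that disagree.

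**3. Grade 1-3 without improvement.** Follow encorafenib through Appendix 3:

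- It is withheld together with binimetinib, for at most 6 weeks (6 × 7 = 42 days).
- Resumption is conditional on improvement, and in this branch that condition is not met.
- Under Section 6.6.1, more than 42 consecutive missed days of encorafenib means permanent discontinuation, and binimetinib must then stop as well.

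Encorafenib therefore stays on hold and, if the hold runs on, is stopped by another rule. What is missing is a statement of its final status at the point where binimetinib is stopped.

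**The case against.** The best defence is that the protocol, read as a whole, already gives the right answer. Every patient starts on both drugs, and Sections 6.6.1 and 6.6.2 send sites to both appendices. Silence in one table does not override an express stop in the other, and Section 6.7 backs that stop. The tables are headed as recommendations and leave room for clinical judgment and labeled guidance. An error would need a site to use one table and overlook both the other table and Section 6.7. Most of this stands, and it is why the point is minor. It does not remove the mismatch at Grade 4, because Section 6.7 refers back to the two tables that differ.

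Three stronger readings are tempting, and the documents do not support them:

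- *Appendix 3 tells sites to keep giving encorafenib.* It says nothing about encorafenib in those lines, and Section 6.6.1 is only permissive. This is an omission.
- *Patients with unresolved Grade 1-3 uveitis would go on taking encorafenib.* The same row has already withheld it and allows a restart only on improvement, and the 42-day rule ends it if the hold overruns.
- *Section 6.7 must be rewritten because some Appendix 3 rows stop binimetinib alone.* Its Grade 4 criterion refers to the appendices, and its missed-dose criterion refers to Section 6.6.1, which is drug-specific. A rewrite letting the appendix row decide would arguably narrow a protective default.

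**Conclusion.** The point holds as a minor safety-consistency correction. There is an explicit conflict between the appendices at Grade 4, and an unstated outcome for encorafenib within Appendix 3 at Grade 1-3. It touches two table lines out of nine shared mandatory-stop rows. The Grade 4 effect is limited by Appendix 2 and Section 6.7, and the Grade 1-3 effect by the conditional restart and the 42-day rule.

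The judgment that both drugs are meant to stop is an inference from Appendix 2, the joint hold, the footnote and the seven other rows; no sentence in Appendix 3 says so. The documents give no uveitis rate, so the number of patients who might be affected cannot be estimated. The ORR hypotheses, rejection thresholds, power and sample size do not depend on these rows.

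**What to change.** In Protocol Appendix 3, have both the Grade 4 uveitis row and the Grade 1-3 line for uveitis that has not improved direct permanent discontinuation of binimetinib and encorafenib. Leave Section 6.7 as it is.

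The cost is two edited table lines, with no new data, visits or procedures. Because these are treatment-stopping instructions, the edit should go through the amendment route in Section 9.1, including ethics approval where patient risk is affected. It can be carried in the next amendment.

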14.1. Definition of AE

| AE Defin | AE Definition | | |
|-----------------|--|--|--|
| • | An AE is any untoward medical occurrence in a patient or clinical study patient, temporally associated with the use of study treatment, whether or not considered related to the study treatment. | | |
| • | NOTE: An AE can therefore be any unfavorable and unintended sign (including an abnormal laboratory finding), symptom, or disease (new or exacerbated) temporally associated with the use of study treatment. | | |

Events Meeting the AE Definition

| ٠ | Any abnormal laboratory test results (hematology, clinical chemistry, or |
|---|---|
| | urinalysis) or other safety assessments (eg, ECG, radiological scans, vital sign |
| | measurements), including those that worsen from baseline, considered |
| | clinically significant in the medical and scientific judgment of the investigator |
| | Any abnormal laboratory test results that meet any of the conditions below |
| | must be recorded as an AE: |
| | |

- Is associated with accompanying symptoms.
- Requires additional diagnostic testing or medical/surgical intervention.
- Leads to a change in study dosing (outside of any protocol-specified dose adjustments) or discontinuation from the study, significant additional concomitant drug treatment, or other therapy.
- Exacerbation of a chronic or intermittent preexisting condition including either an increase in frequency and/or intensity of the condition.
- New conditions detected or diagnosed after study treatment administration even though it may have been present before the start of the study.
- Signs, symptoms, or the clinical sequelae of a suspected drug-drug interaction.
- Signs, symptoms, or the clinical sequelae of a suspected overdose of either study treatment or a concomitant medication. Overdose per se will not be reported as an AE/SAE unless it is an intentional overdose taken with possible suicidal/self-harming intent. Such overdoses should be reported regardless of sequelae.
- The signs, symptoms, and/or clinical sequelae resulting from lack of efficacy will be reported as an AE or SAE if they fulfill the definition of an AE or SAE

Events Meeting the AE Definition

and meet the requirements as per Section 7.5. Also, "lack of efficacy" or "failure of expected pharmacological action" does not constitute an AE or SAE

Events NOT Meeting the AE Definition

- Any clinically significant abnormal laboratory findings or other abnormal safety assessments which are associated with the underlying disease, unless judged by the investigator to be more severe than expected for the patient's condition.
- The disease/disorder being studied or expected progression, signs, or symptoms of the disease/disorder being studied, unless more severe than expected for the patient's condition.
- Medical or surgical procedure (eg, endoscopy, appendectomy): the condition that leads to the procedure is the AE.
- Situations in which an untoward medical occurrence did not occur (social and/or convenience admission to a hospital).
- Anticipated day-to-day fluctuations of preexisting disease(s) or condition(s) present or detected at the start of the study that do not worsen.
- Worsening of signs and symptoms of the malignancy under study should be recorded as AEs in the appropriate section of the CRF. Disease progression assessed by measurement of malignant lesions on radiographs or other methods should not be reported as AEs.

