7.3.6. Vital Signs

Vital sign measurements (should be taken before blood collection for laboratory tests or at least 30 minutes after blood collection for laboratory tests), will be measured per institutional standards as part of the physical examination at the time points specified in SoA (Table 3). Vital sign assessments include the following:

- Temperature, pulse rate, respiratory rate, and blood pressure will be assessed.
- Blood pressure will be assessed with the patient in a recumbent, semi recumbent, or sitting position. Manual techniques will be used only if an automated device is not available. Blood pressure and pulse measurements will be preceded by at least 5 minutes of rest.

All vital sign measurements occurring on dosing days must be performed prior to study drug administration. Abnormal vital sign results identified after the first dose of study treatment constitute an AE if they are considered clinically meaningful, induce clinical signs or symptoms, require concomitant therapy, or require changes in study drug/treatment.

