7.6.4. Adverse Events

Treatment-emergent adverse events (TEAEs) are defined as AEs with onset date during the on-treatment period.

Unless otherwise stated, only TEAEs will be presented in summary tables. However, all AEs will be presented in listings. AEs and SAEs will be coded by PT and SOC using the latest available MedDRA version.

The severity of an AE will be assessed by the investigator using the NCI CTCAE, Version 4.03. For participants with more than 1 AE within a SOC or PT, only the highest grade will be included in by-severity summaries.

The investigator will also assess whether the AE is related to study drugs (i.e., a treatment-related AE). For participants with more than 1 AE within a SOC or PT, the highest level of relationship (related is higher than not related) will be included in the by relationship summaries. AEs will be considered treatment related if they are related to encorafenib and/or binimetinib.

For summaries by SOC and PT, each participant will be counted at most once per SOC and at most once per PT. For summaries by PT, each participant will be counted at most once per PT.

Overall summary of safety table will include numbers and percentages of the following:

- Participants with at least 1 TEAE regardless of causality
- Participants with at least 1 treatment-related TEAE
- Participants with Grade 3 or 4 TEAEs
- Participants with Grade 3 or 4 treatment-related TEAEs
- Participants with Grade 5 TEAEs
- Participants with Grade 5 treatment-related TEAEs
- Participants with at least 1 treatment-emergent SAE
- Participants with at least 1 treatment-related SAE
- Participants who discontinued study drug due to a TEAE regardless of causality
 - TEAE leading to encorafenib discontinuation
 - TEAE leading to binimetinib discontinuation
- Participants with a dose reduction due to a TEAE
 - TEAE requiring encorafenib dose reduction
 - TEAE requiring binimetinib dose reduction
- Participants with a dosing interruption due to a TEAE
 - TEAE requiring encorafenib dosing interruption
 - TEAE requiring binimetinib dosing interruption

All TEAE summaries will be displayed (frequency counts and percentages) alphabetically by system organ class (SOC) and preferred term (PT) by descending frequency within SOC

based on “Total” group, if not otherwise noted. Individual summary tables showing the incidence of participants with the following subsets of TEAEs will be generated:

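### A protocol-specified dose change does not by itself make a laboratory abnormality a recordable AE, so some such changes could be missing from the SAP's TEAE dose-change rows

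*Protocol*

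**What the plan says.** Protocol Appendix 4, Section 14.1 gives several routes by which a laboratory result becomes an AE. A result meets the definition if it is considered "clinically significant in the medical and scientific judgment of the investigator". It must also be recorded if any listed condition applies. These include "Is associated with accompanying symptoms", "Requires additional diagnostic testing or medical/surgical intervention", significant added treatment, and the dosing condition, "Leads to a change in study dosing (outside of any protocol-specified dose adjustments) or discontinuation from the study".

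The dose-modification appendices use different language. Both are titled as guidance for adverse events, and the column holding the triggers is headed as AE severity. Laboratory findings sit in that column: AST or ALT increases in both appendices, and in Appendix 3 a CPK row that opens "Grade 4 asymptomatic CPK elevation or". A catch-all row covers recurrent Grade 2 events, "First occurrence of any Grade 3", and Grade 4. Section 6.6.2 likewise speaks of dose reductions as the result of an AE.

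Section 7.3.6 makes an abnormal vital sign an AE if, among other things, it should "require concomitant therapy, or require changes in study drug/treatment". It has no exception for changes that the protocol itself specifies.

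SAP 7.6.4 defines TEAEs as AEs with onset in the on-treatment period. Its overview includes "Participants with a dose reduction due to a TEAE", a matching row for interruptions, and tables by preferred term and by drug.

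**The concern.** Two sites can follow the protocol in good faith and record the same event differently. One reads Appendix 2 or 3, sees the finding classed as an AE, and records it. The other reads Section 14.1, sees that the dose change was protocol-specified, and does not. Whether the patient then counts in the SAP rows for dose changes attributed to a TEAE depends on which section the site consulted.

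This matters because AE incidence and severity is a secondary endpoint, the protocol's rationale relies on a differentiated safety profile, and the amendment history says the study was revised to support registration. With a single treatment regimen there is no concurrent arm in which the same under-recording would cancel out. The possible error runs in one direction, towards a more favourable TEAE dose-change rate.

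**Working it through.** The documents state no figure for this quantity, so there is none to reproduce. The check is a reading of the sections against each other, followed by an illustration of scale.

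**Step 1. One case under each rule.** Take an asymptomatic Grade 3 laboratory value (hyponatremia, say) that the investigator attributes to study drug and manages under the catch-all row with a hold and then a reduced dose.

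| Rule | Is an AE record required? |
|---|---|
| Appendices 2–3, Section 6.6.2 | The finding is treated as an AE |
| 14.1, symptoms | No, there are none |
| 14.1, further testing, intervention or significant added treatment | No, if none is needed |
| 14.1, dosing change | No, because the change is protocol-specified |
| 14.1, clinical significance | Left to the investigator |
| 7.5.1, treatment stopped for an AE | Yes, but only if the finding is already classed as an AE |

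So 14.1 can leave the record to judgment where the appendices presume it. Section 7.5.1 does not settle the matter: it requires recording when treatment is stopped temporarily or permanently because of an AE, which assumes the classification in question, and it does not name reductions. A vital sign leading to the same change would be an AE outright under 7.3.6.

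**Step 2. Where the event goes.**
- SAP 7.6.4 reduction and interruption rows: not counted without an AE record.
- SAP 7.6.1.1: counted, with its reason, from the dosing eCRF.
- SAP 7.6.5 shift and worst-grade tables: counted from laboratory data.

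No step in the SAP reconciles the first with the second.

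**Step 3. Scale, under assumptions.** The fall in the TEAE dose-change rate, in percentage points, is r × h × u × (1 − c), where
- r = rate of the abnormality,
- h = share leading to a hold or reduction,
- u = share of those with no AE record,
- c = share of those patients already counted through another TEAE-linked change.

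The documents give only r, and only from the melanoma study (Protocol 2.1.4: Grade 3–4 ALT 6%, CPK 5%). Set h = 1 and c = 0, both of which push the result up. The lower end of each range is ALT alone. The upper end is ALT plus CPK without overlap, 6 + 5 = 11%.

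| u | Fall (points) | Patients of 97 | Patients of 107 |
|---|---|---|---|
| 0 | 0 | 0 | 0 |
| 0.25 | 1.5–2.8 | 1.5–2.7 | 1.6–2.9 |
| 0.50 | 3.0–5.5 | 2.9–5.3 | 3.2–5.9 |
| 1.00 | 6.0–11.0 | 5.8–10.7 | 6.4–11.8 |

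Here 97 = 60 + 37, and 107 is the expected maximum enrolled. The last row is a ceiling for these two tests at Grade 3–4. It is unlikely to be approached, because the protocol adds monitoring for transaminases above 3 × ULN (Appendix 5) and weekly tests for CK at or above 3 × ULN (Table 11), which may meet the further-testing condition. Grade 2 AST/ALT holds are left out, since no rate is given.

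The tests that reach a dose change only through the catch-all row are glucose 5%, creatinine 4%, anemia 4%, hyponatremia 4%, neutropenia 3% and lymphopenia 2%. These sum to 22 per 100, or 107 × 0.22 = 23.5 abnormalities. That is a sum of rates with overlap ignored, regardless of cause or dose change. With h and u unknown, it fixes no lower limit above zero.

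**The case against.** The strongest reply is that the gap hardly exists. Anything in Appendices 2–3 is already an AE, so Section 7.5.1 requires it to be recorded when treatment is held or stopped. A value serious enough to change dosing will nearly always be judged clinically significant; for non-protocol local tests, Section 7.3.9 even gives dose modification as an example of significance. The catch-all row applies to adverse reactions, so the finding must already be seen as one. Section 6.6.1 leaves holds to clinical judgment and may exempt transient laboratory values from the dose-reduction rules. The appendices are recommendations, and Section 6.6 also points to labelled and institutional guidance, so some changes may not be protocol-specified at all. Findings due to the underlying disease may not be AEs in any case.

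Most of this stands as a limit on size. It does not remove the conflict. If every appendix trigger is an AE, the exception in 14.1 contradicts the appendices; if not, recording is optional for some events that change dosing. The 7.3.9 example governs entry of a result in the eCRF, not its classification as an AE.

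A reader might infer something stronger: that Appendix 4 exempts laboratory abnormalities from AE recording, or that the TEAE dose-change rate is understated by a definite amount. The documents support neither. The exception removes one trigger and leaves clinical significance, symptoms, further testing or intervention, and significant added treatment in force. No document says how many laboratory-only dose changes occur or what share goes unrecorded.

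**Conclusion.** The inconsistency is real and modest in weight. Section 14.1 does not count a protocol-specified dose change as a reason to record a laboratory abnormality, while Appendices 2–3 and Section 6.6.2 treat the same findings as AEs and 7.3.6 has no matching exception. The exposure is confined to asymptomatic holds or reductions that meet none of the other conditions in 14.1, and to the SAP 7.6.4 rows and term-level TEAE counts that depend on an AE record. Overall dose modifications and laboratory grades are reported independently of AE recording, and no efficacy endpoint is touched.

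The understatement cannot be computed and may be zero. The illustration in the working rests on melanoma rates carrying over, every such abnormality changing the dose, no patient being counted already for another reason, and an assumed unrecorded share anywhere from 0 to 100%. It shows scale and is not an estimate of bias.

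**What to change.** For data already collected, add one SAP listing that matches each reduction or interruption in 7.6.1.1, by its recorded reason, to the AE records, and report those with no linked AE beside the 7.6.4 tables. The documents do not show whether the dosing form has a separate laboratory reason; if it does not, list every unlinked change with the reason as entered. The listing comes first because much of the enrolment is likely to have taken place: SAP version 3.0 follows an interim analysis planned at about 54 of 60 treatment-naïve participants. If few changes are unlinked, the TEAE tables are confirmed.

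In the protocol, reconcile 14.1 with Sections 6.6.2, 7.3.6 and 7.5.1 and Appendices 2–3 by deleting the parenthetical exception, so that a laboratory abnormality leading to a hold, reduction or discontinuation of either drug is recorded as an AE.

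The cost is one listing, one clarified phrase, a few more AE records, a slightly less favourable TEAE rate, and a note in the report that earlier patients were recorded under the previous wording. No change to any dose rule is proposed.
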